- Subjects must be able to perform all of their activities of daily living (ADL) with only minimal use of ambulatory aids. Subjects may use a narrow-base cane (single point, narrow tripod base, etc.) as an ambulatory aid in any amount. Use of more comprehensive ambulatory aids (e.g. a small-base quad cane, wide-base quad cane or walker) must be limited to no more than 20% of their walking time when not at home. Individuals who do use an assistive device occasionally should report a threshold for use of greater than 100 feet, i.e., they are unlikely to use their device unless they anticipate ambulating greater than this distance.

Exclusion criteria:

Target Populations:

- Allergy to electrode gel, surgical tape and metals.
- Subjects who currently use the Bioness L300 Go or similar neuro-orthoses or use a carbon fiber ankle-foot orthosis for more than occasional use at the time of the study will be excluded to avoid biasing results for one device or the other. Occasional use for the purpose of this study is defined as more than 20% of walking time when not at home. Subjects with past experience who are not currently using these devices will be eligible.
- Subjects enrolled in physical therapy or other rehabilitative care for treatment of gait, balance, or lower extremity strength or coordination at the time of the study will be excluded to avoid confounding effects from therapy and device-based management of their condition.
- For the orthotics study, subjects with peripheral neuropathy impacting control of the tibialis anterior muscle via the peroneal nerve will be excluded.

- Subjects under treatment for infectious diseases will be excluded from the study.
- Women who are pregnant or planning to become pregnant during the course of the study will be excluded.
- Symptomatic musculoskeletal conditions that prevent unaided walking, such as back pain or knee arthritis.
- Cardiovascular conditions that make moderate exercise unsafe, including (but not limited to) history of angina, peripheral vascular disease, congestive heart failure, history of myocardial infarction, and history of stroke. Potential participants will be excluded if they self-report that a physician has told them to avoid moderate exercise.
- History of chest pain, shortness of breath, or claudication symptoms during ambulation
- History of significant neuropathy with altered balance
- History of serious residual limb pain or phantom limb pain within the past six months.

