Subjects with amputation will use their own prostheses and/or standard commercially available prostheses (**Figure 1**). No experimental devices will be used in this study.

Subjects with drop-foot will use the Bioness L300 Go functional electrical stimulation neuro-orthoses or the Thuasne SpryStep, a standard carbon fiber orthosis (**Figure 2**).

To test prostheses on unimpaired subjects, these subjects will wear a “prosthesis simulator” system. One version is prosthesis simulator boots – rigid walking boots that immobilize the ankle similar to ski boots, with a special attachment on the bottom surface to simulate walking with a prosthetic foot. These experimental simulator boots have been used in past human research by the PI and others [18]–[21]. Other variations of a prosthesis simulator system may also be used, such as versions based on leg braces that circumvent the ankle rather than immobilizing it.

Unimpaired subjects may also test standard AFO's by wearing them with standard footwear. All standard devices will be purchased off-the-shelf. Standard custom orthoses (e.g. AFO's constructed to fit individual patients according to standardized procedures) will be constructed at the UW Health Orthotics and Prosthetics Clinic.

Biomechanically unimpaired subjects may also test wearable sensors through comparisons of different kinds of footwear.

The sensors used in the study have no action that could affect the subject, and their effects are not under investigation. They are for instrumentation only, and therefore are not investigational devices.

Instructions:

We will provide subjects with instructions for using the sensors and test devices (prostheses/orthoses/footwear). Information will include: how to turn on the sensors and test devices; how to plug in and charge any that need power; when they should or should not be used; how to keep them clean; what to do if certain problems arise; and contact information for the study team members whom subjects should contact if they have any questions or problems with the devices.

Analyses:

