Finally, we will use custom questionnaires to gauge the utility of the devices under test. For the MS group, custom questionnaires will also be utilized to rate their daily fluctuations in fatigue and to communicate which shoes they utilized for the day, which is necessary as this impacts data interpretation. These questionnaires will be administered either on paper or on a computer by web form (e.g. using REDCap, Qualtrics™ or other tools compliant with HIPAA requirements). The subject code, but no other identifying information, will be collected on the form. Questions will be specific to each device or group of devices tested, because each is designed based on a different concept. Each questionnaire will be submitted for IRB review and approval prior to use with subjects.

Questions may include ratings (e.g. 0-10 ratings, visual analog scales, etc.) or rankings (e.g., best to worst, 1 to 5, etc.) of comfort, discomfort, utility, preference, pain, performance, fatigue, and specific features of the device's perceived biomechanical behavior. For example, we may ask subjects to "rate the quality of forefoot rollover movement with this prosthesis," or to "rate the severity of the mid-stance 'flat spot' you perceive with this orthosis," or "rate how comfortable would you feel relying on this device to walk along a forest trail." We will also include an optional space for open comments, because user comments provide deep insight into how these kinds of devices can be improved. The surveys will exclude sensitive questions, including but not limited to: embarrassing, damaging, personal or invasive information; information that could potentially

identify the respondent; protected health information; detailed information about any health condition or disability.

Outcome Measures

Outcomes will generally be compared using a repeated-measures design, in which each subject acts as his/her own control. This design is chosen to minimize the statistical problems caused by heterogeneity in the subject population.

- Ground Reaction Force (GRF): force applied by the body to the ground. Peak forces and shape of the force vs. time trajectory are commonly used to assess gait quality. Forces closer to “normal” are usually considered better, but this goal may not apply in persons with amputation.

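### The exclusion for current orthosis users defines occasional use as above 20% of walking time, so as written it excludes no carbon fiber AFO user, the opposite of its evident intent

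*Combined protocol and SAP*

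**What the plan says.** The rule is a single bullet under Exclusion criteria, Target Populations. It applies to "Subjects who currently use the Bioness L300 Go or similar neuro-orthoses or use a carbon fiber ankle-foot orthosis for more than occasional use", judged on present habits, and its stated consequence is that these people "will be excluded to avoid biasing results for one device or the other". The next sentence supplies the operative definition: "Occasional use for the purpose of this study is defined as more than 20% of walking time when not at home". The bullet closes with an allowance for former users: "Subjects with past experience who are not currently using these devices will be eligible".

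The Devices section shows why these device types are singled out: "Subjects with drop-foot will use the Bioness L300 Go functional electrical stimulation neuro-orthoses or the Thuasne SpryStep, a standard carbon fiber orthosis". They are the two conditions to be compared in the drop-foot branch.

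No other section defines occasional use or corrects this definition. The sentence is complete and grammatical, so lost or redacted text does not explain it.

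**The concern.** The exclusion turns on one term, and the definition of that term points the wrong way. A screener who follows it admits an everyday wearer of a carbon fiber AFO. A screener who applies the obvious purpose turns that person away and departs from the text.

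What is at stake is the comparison between the two orthotic devices. Under Outcome Measures the design is one "in which each subject acts as his/her own control". Pairing removes stable differences between people. It does not remove a difference between one person's own two conditions, and a current habit with one of the two devices is exactly that. The protocol's purpose clause recognises the problem. Its section on real-world movement assessment also criticises laboratory studies for often testing people before they have adapted to a new device, though that remark concerns existing research in general.

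The orthotics branch serves the secondary objective. The primary outcome under Specific Procedures, stride length at identical walking speed, also covers orthoses and carries an expected increase with the stimulation device. With a target of 10 drop-foot subjects, one habitual AFO user admitted against the intent would be 1/10 of the planned group.

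**Working it through.** The plan gives no figure to reproduce here. The check is a logical reading of the criterion.

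**Inputs**

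- Trigger: current use beyond occasional (Exclusion criteria, Target Populations).
- Definition: occasional means more than 20% of out-of-home walking time, with no upper limit (same bullet).
- Purpose and former-user clause: same bullet.
- Comparators: a neuro-orthosis and a carbon fiber AFO (Devices).

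**Step 1: the text as written.** Let *s* be the share of out-of-home walking done with the carbon fiber AFO, 0 < *s* ≤ 100%. Occasional use is the set 20% < *s* ≤ 100%. To be more than occasional, *s* would have to lie above that range, so *s* > 100%. That is impossible, and the excluded set is empty.

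**Step 2: the text with the direction reversed.** Occasional use is *s* ≤ 20%. The excluded set is 20% < *s* ≤ 100%.

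**Step 3: the two readings side by side.**

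| AFO share *s* | As written | Direction reversed |
|---|---|---|
| 20% or less | eligible (below occasional) | eligible (occasional) |
| 21% | eligible (occasional) | excluded |
| 60% | eligible (occasional) | excluded |
| 100% | eligible (occasional) | excluded |

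The readings differ for every *s* above 20% and nowhere else. These are logical sets; they say nothing about how many candidates fall in each.

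**Step 4: which direction was meant.** Three points agree.

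1. The purpose is to avoid bias toward one device, and an empty exclusion cannot serve it.
2. The sentence that keeps former users eligible presupposes that current use can disqualify.
3. The Multiple Sclerosis inclusion criterion says that use of quad canes and walkers "must be limited to no more than 20% of their walking time when not at home". That is the same percentage and the same denominator, set as a cap. It continues: "Individuals who do use an assistive device occasionally should report a threshold for use of greater than 100 feet". This support is indirect, because it concerns other aids.

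**Step 5: scope of the allowance.** The bullet repeats its verb, so the qualifier may apply to both device types or to the AFO alone.

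- If it covers both, the literal exclusion is empty for neuro-orthosis users as well.
- If it covers only the AFO, any current neuro-orthosis user is excluded whatever the share.

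The AFO result in Steps 1 to 3 is the same either way. The plural reference to these devices in the former-user sentence and the symmetric purpose favour covering both, but the text does not settle it.

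**The case against.** The strongest reply is that the meaning can be recovered on the page. The definition directly follows the phrase it serves, in a bullet whose purpose is stated, and the literal reading empties the rule. A sensible screener would therefore reject that reading, and this is close to a wording slip. Much of that stands, and it limits the severity. It does not make the text correct. This is an explicit study definition of an eligibility threshold, and the screening script that might show actual practice is an attachment outside the documents.

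It can also be said that no harm is shown and that familiarity may matter less here, because each device is worn for one to three weeks of everyday life. The first part is true: neither the direction nor the size of an effect can be derived. The second is possible, but the documents do not show that such a period removes the advantage of an established habit.

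Finally, the correction removes only part of the prior-experience problem. Former users and users at or below 20% stay eligible on either reading. So do habitual users of plastic AFOs, although the background section on orthoses describes the comparator as plastic or carbon fiber, and Test Conditions speaks only of a standard orthosis. That is a fair limit on what the fix achieves, and no reason to leave the definition inverted.

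**Conclusion.** The concern holds. As written, the carbon fiber AFO exclusion covers no level of use; read as evidently meant, it covers all use above 20% of out-of-home walking. The AFO conclusion needs no assumption beyond the plain wording of the bullet and holds under either reading of the allowance's scope. Whether the allowance extends to neuro-orthoses is a point to clarify, not an error.

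The reach is the drop-foot group, with target enrollment of 10. The 10 is a target and not a ceiling. The consequence cannot be quantified: the documents give no distribution of current device use and no familiarity effect, and whether anyone was wrongly admitted is unknown. No sample size, power or alpha figure changes. This should be fixed, because an operative eligibility cut-off contradicts its own stated purpose.

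**What to change.** 1. In the definition, change *more than* 20% to *no more than* 20%. This keeps the protocol's own figure and denominator and makes use above 20% disqualifying.
2. In the same bullet, state whether the allowance for occasional use covers neuro-orthoses and carbon fiber AFOs alike, or the AFO only.
3. Confirm that the screening script uses the same direction and the same scope.
4. Review enrolled drop-foot subjects against the corrected rule. Telephone-screening answers are kept in REDCap (Subject Recruitment), and prescribed-device specifications are recorded (Privacy and Confidentiality). Neither section lists share of use, so report as not assessable any subject for whom it was not captured.

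The cost is a one-bullet amendment, a script check, and a record review for a group with a target of 10.

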We will perform laboratory testing at the beginning and end of the period using each device, except in the cases of individuals using their own devices whose schedules or locations necessitate off-site installation (no lab testing for these individuals – they will complete the take-home portion of the study only). For each device, we will perform standard gait and movement analysis. During field testing and take-home testing, participants' locations and motions will be recorded with a combination of global positioning system (GPS), wearable inertial measurement unit (IMU), Bluetooth and Wifi network sensors. During take-home testing, data will be recorded continuously during all waking hours when the participant uses the sensors. Unimpaired subjects may also be invited to participate in the take-home study to provide normative data with different types of footwear. Take-home portions of the study will last at most 10 weeks. Subjects in the off-site installation group will only perform everyday-use testing, in which wearable sensors on their existing prostheses (and potentially cell-phone GPS) log data while they use each of their prostheses.

Figure 2: Orthotic drop-foot aids for potential use in the experiment: an ankle-foot orthosis (left), BioNess FES Neuroorthosis (right). The Bioness FES device senses leg motion and stimulates the peroneal nerve during swing

phases of gait, causing the dorsiflexor muscles to lift the foot for improved ground clearance.

Biomechanically intact persons will perform normal locomotion activities such as standing, walking and running, while standard and novel biomechanical measurements are taken. The activities may include some or all of the following:

- Standing still, with eyes open or closed, on flat or sloped surfaces that are stiff (normal) or soft. These standing activities may be performed on standard force plates or on a force plate that estimates stability from characteristics of the ground reaction force signals under the feet and moves the surface and a visual surround to perturb balance.
- Walking at a range of speeds, forward or backward, on flat, uphill, downhill, or side-hill surfaces, or stairs. Surfaces may include indoor and outdoor ground, and/or an instrumented treadmill that measures ground reaction forces under both feet.
- Running in all the same conditions as walking.
- Performing any of these activities barefoot or with various shoes or boots.

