- Performing any of these activities using "prosthetic simulators" on one or both legs. Prosthetic simulators are designed to allow an intact person to use a foot-ankle prosthesis by holding the natural foot out of the way.
- Performing any of these activities spontaneously while wearing long-term monitoring sensors in everyday life.

Persons with lower-limb amputation will perform all the same tests described above in biomechanically intact individuals, but using a variety of commercially-available lower-limb prostheses. The prostheses may be of many kinds exhibiting different behaviors and properties, including but not limited to:

- Standard wood, plastic and foam prostheses.
- Carbon fiber or fiberglass prostheses with high energy storage and return.
- Prostheses with passive or manually-adjusted mechanisms to alter properties such as stiffness or damping.
- Prostheses with microprocessors that control their motion or properties such as stiffness, damping or joint angle through active adjustment.
- Running-specific and other activity-specific prostheses.

Running tests will be limited to those who are already habitual runners.

Persons with drop-foot will perform all the same tests as those with lower-limb amputation, using different orthotic solutions. The orthotic solutions may include braces of various kinds as

well as neuro-orthoses, including but not limited to:

- Standard orthoses, made of plastic, fiberglass or carbon fiber, with or without hinges.
- Custom orthoses with special structural features such as custom stiffness, novel support surfaces, or energy return properties.
- Functional electrical stimulation (FES) devices that stimulate the peroneal nerve to activate the ankle dorsiflexor muscles.

Orthoses may be designed and built by orthotists associated with the study team according to standard clinical practices, or they may be purchased off-the-shelf according to standard clinical prescription practices. Running tests will be limited to those who are already habitual runners.

The subgroup of persons with Multiple-Sclerosis and drop-foot will perform all procedures as described for persons with drop-foot, but enrollment will be restricted to MS patients.

All participants may be subjected to a variety of measurements:

- Weight and size measurements for scaling biomechanical models.
- Use of skin-mounted reflective markers for motion capture in a research-grade motion laboratory.

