Specific Procedures – Comparing Prostheses and Orthoses using Real-World Data

Study Design:

Subjects will wear one or more movement sensors on various body segments, especially the foot, as well as means of logging location data (e.g. a GPS, Bluetooth, Wifi receiver and/or cell phone app). Subjects will wear (movement sensors) and/or carry (phone) these sensors during extended measurement periods of up to three weeks per experimental condition, for up to four conditions (prostheses, orthoses or footwear). We will combine movement and location data to identify the most-frequently-repeated paths a person takes, and finally analyze movement along these paths to identify changes in mobility performance (**Figure 6**). We will also perform standard biomechanical analyses of posture and movement in the laboratory.

NOTE: Because part of this study is the development of these methods, we may change the number of sensors, which sensors are used, how they are worn/carried, how long the take-home tests are, the devices under study, and other details of the study, within the limits approved in the *Study Procedures – General* section of this protocol.

[figure not shown]

Figure 6: Example self-test by the experimenters showing highly repeated straight walking trajectories found from a 10-day walking test. The experimenter wore athletic shoes and sandals for 5 days each, indicated by solid lines and dashed lines respectively. The same color indicates same paths. Blue and red lines are walking trajectories in the hallway between the subject's office and the restroom and water fountain (different directions are separated into two different paths). Yellow lines represent the sidewalk between the building where the subject works and a nearby bus stop. Purple lines represent a sidewalk between the same building and a dining location.

Test Conditions:

- Prosthetics branch 1: Participants with amputation will use 2-4 prosthetic feet from different categories, each fit to their standard socket by a professional prosthetist.
 - Participants will use each prosthesis for a take-home test of 1-3 weeks of everyday life. Comparisons will include energy-storage-and-return prostheses (ESR) vs. prostheses with a passive hydraulic ankle (PHA) vs. prostheses with a microprocessor ankle (MPA) (**Figure 1**). Comparisons may also include Articulated ESR (AESR) prostheses, which have one or more additional joints in the mechanism, or other types of standard commercial prostheses.

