- Most likely measurements include: miniature inertial sensors, GPS, Bluetooth and Wifi location from a wearable receiver or cell phone app, force plate/force treadmill, EMG, motion capture, indirect calorimetry, and voice/photo/video recording.

Intended Outcome - Primary:

The primary outcome is the measured difference in stride length at identical walking speed when using different prostheses, orthoses, or footwear. We expect to observe increased stride length when using more compliant prostheses or the FES neuro-orthosis.

Intended Outcomes - Secondary:

The secondary outcomes include other measures of gait performance determined from the same system. Stride width, stride clearance, speed, stride frequency, ground reaction forces, and measures of gait regularity are among many analyses that will be performed with the data from this experiment.

Data and Safety Monitoring Plan

The PI will oversee compliance with the data and safety monitoring plan to ensure adherence to IRB guidelines. All researchers and research staff involved in the study are required to maintain Human Subjects and HIPAA training and will be continuously involved in data and safety monitoring. Data and safety monitoring will occur on a continuous basis.

Adverse events or problems will be reviewed by the principal investigator as they occur and reported to the IRB in accordance with posted guidelines at the “Events Requiring Reporting to the IRB” page: <https://kb.wisc.edu/hsirbs/18324>.

Data Processing/Data Analysis:

Electromyographic, kinematic, kinetic, and metabolic data will be compared with different lower limb prostheses, orthoses and footwear, using repeated measures ANOVAs. In initial experiments measuring movement performance with only the subject’s own devices, we will use repeated measures ANOVAs to compare performance variables (e.g. EMG amplitude, gait economy, joint range of motion, peak ground reaction force) under different conditions (e.g. locomotion speed, incline, motor task). Corrections for multiple comparisons will be made using False Discovery Rate adjustments [51], [52]. In analysis of experimental conditions, we will use the new methods developed in this research for analyzing the same types of movement information, isolated to frequently-repeated paths in everyday life. We may also analyze specific events of interest such as slips, trips or falls that occur in everyday life and are recorded by the wearable sensors [53].

Sample size

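### Daily shoe use is planned to be recorded only in the MS group, so in the other take-home patient groups a shift in shoes between device periods could not be checked

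*Combined protocol and SAP*

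**What the plan says.** The shoe record appears once, in Assessments, Surveys and Feedback. The sentence opens with "For the MS group, custom questionnaires will also be utilized to rate their daily fluctuations in fatigue" and goes on to have the same participants "communicate which shoes they utilized for the day, which is necessary as this impacts data interpretation". The clause about necessity may refer to fatigue and shoes together; on either reading it includes shoes.

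The outcome concerned is in the real-world procedures, Intended Outcome - Primary: "The primary outcome is the measured difference in stride length at identical walking speed when using different prostheses, orthoses, or footwear". Test Conditions sets the exposure for both prosthetics branches: "Participants will use each prosthesis for a take-home test of 1-3 weeks of everyday life". Outcome Measures gives the design: "Outcomes will generally be compared using a repeated-measures design, in which each subject acts as his/her own control".

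Footwear is also a test condition in its own right. Participants without impairment compare types of footwear, and in the Figure 6 example "The experimenter wore athletic shoes and sandals for 5 days each". The activity list in Research Design and Methods allows "Performing any of these activities barefoot or with various shoes or boots", and the same section then says "Persons with lower-limb amputation will perform all the same tests described above in biomechanically intact individuals".

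**The concern.** Daily fatigue is a natural MS-specific item. The stated reason for recording shoes, that they affect how the data are read, is not specific to MS. Nothing in the protocol explains why shoes would matter for a participant with MS and drop-foot but not for one with drop-foot from another cause, or for a prosthesis user.

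The prosthesis comparison serves the primary objective, and its take-home part runs unsupervised for weeks per device. Using each person as his or her own control removes stable differences between people. It does not remove a change of shoes within a person from one device period to the next. No randomised or counterbalanced device order is described, so a drift in shoe habits over time could line up with device. If it did, part of a stride-length difference credited to the device would belong to the shoes, and the planned data could not show it.

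**Working it through.** **1. Is there another safeguard?** These are the places where one could sit:

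- *Real-World Movement Assessment*: comparable bouts are defined by path, across days and conditions. Shoe is not a matching variable.
- *Measurements list* (Research Design and Methods): voice recordings are for notable events, and shoes are not among the examples.
- *Test Conditions*: shoes are not held constant across devices. In prosthetics branch 2, one installation visit is enough and sensors may come back by mail, so staff may not see the participant's shoes again.
- *Assessments, Surveys and Feedback* and *Outcome Measures*: custom questionnaires are open in content, but a shoe item is stated only for the MS group.
- *Data Processing/Data Analysis*: repeated-measures ANOVA, and new methods confined to often-repeated paths. Footwear is named as something to compare, not as a covariate or stratum in the patient comparisons. No analytic use of the MS shoe record is stated either.
- *Minimizing Risks*: weekly calls cover device problems, adverse effects and pregnancy.

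None of them records shoes, standardises them or matches on them for the other patient groups.

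**2. The plan's own figures.** The Sample size section gives N = 2 × ((1.96 + 0.84) × σ/d)².

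- Push-off: 2 × (2.80 × 1.5/3.1)² = 3.67, rounded up to 4.
- Collision work: 2 × (2.80 × 0.04/0.055)² = 8.29, rounded up to 9.

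Both reproduce, and this point does not dispute them. Neither concerns stride length or shoes. Only the planned n of 10 is carried forward.

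**3. Possible bias in centimetres.** Bias = shoe effect on stride length × difference between device periods in the share of bouts walked in that shoe. The documents give neither input, so both are assumptions.

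| Assumed shoe effect | Shift 20 points | Shift 50 points | Shift 100 points |
|---|---|---|---|
| 1 cm | 0.2 cm | 0.5 cm | 1.0 cm |
| 2 cm | 0.4 cm | 1.0 cm | 2.0 cm |
| 4 cm | 0.8 cm | 2.0 cm | 4.0 cm |

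The documents give no standard deviation or expected device effect for stride length, so these figures cannot be compared with the effect sought.

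**4. What a bias would do to a test.** As an illustration, take a paired t-test with n = 10, two-sided 5%, and no true device effect. Express the average shoe bias b in SDs of the within-person device difference. The noncentrality is b × √10.

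| b | Example giving this b | False-positive rate |
|---|---|---|
| 0 | no imbalance | 5.0% |
| 0.1 | 10-point shift × 1 SD shoe effect | 5.9% |
| 0.25 | 50-point shift × 0.5 SD | 10.9% |
| 0.5 | 50-point shift × 1 SD | 29.3% |
| 1.0 | 100-point shift × 1 SD | 80.3% |

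**5. If the imbalance averages zero across people.** There is then no bias, only added variance. With a true effect of 1 SD and n = 10, power is 80.3%. Adding shoe variation with SD v inflates the SD by √(1 + v²). Power becomes 77.9% for v = 0.25, 71.2% for v = 0.5 and 51.4% for v = 1.0.

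**The case against.** Much of the case on the other side stands, and it limits the point.

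- A reader might infer that the other groups are never asked about shoes. The protocol supports only that no such question is planned. The custom questionnaires are not shown, and the protocol reserves some freedom to change study details. Still, each questionnaire needs ethics approval before use, so permission to ask is not a plan to ask.
- A reader might infer that the information is lost for good. The weekly calls and, in prosthetics branch 1, the visits around each period would allow coarser capture after the fact. Neither is described as covering shoes.
- A reader might infer that the protocol holds that footwear changes stride length. It lists footwear as a condition to compare. Its stated expectation of longer strides covers only more compliant prostheses and the FES neuro-orthosis.
- If a device needed a particular shoe, that shoe would be a consequence of the device and part of its effect as used, not a confounder. No section says that a study device needs one. Given the stated aim of ecological validity, making same-shoe bouts the primary analysis would change the question being asked.
- A drift in shoe habits over weeks biases the contrast only if it lines up with device order in the same direction across participants.
- Study Outcomes defines the primary outcome more broadly, and much of it is measured in supervised laboratory sessions where staff can see the shoes. The exposure here is take-home stride length. Matching on path and speed also removes any shoe effect that acts through those two.
- The number of drop-foot participants without MS is not stated. The target is 10 with drop-foot in all, so that group may be small.

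What remains is the gap itself. The protocol gives a reason for a shoe record that is not MS-specific, then plans the record for the MS group alone.

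**Conclusion.** The point holds as a cheap improvement. For prosthesis users and drop-foot participants without MS, the protocol provides no means of telling whether shoe use differed between take-home device periods.

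The documents do not support the stronger conclusion that the prosthesis comparison is confounded by footwear. Bias needs a systematic shift in shoe use with device or period, and nothing shows that one will occur. Its size is unknown. The range of 0.2 to 4 cm rests wholly on an assumed shoe effect of 1 to 4 cm and an assumed shift of 20 to 100 points. In the illustrative test, small imbalances hardly matter (5.9% false positives at 0.1 SD). Moderate systematic ones do (29.3% at 0.5 SD). Unsystematic variation costs power only. No sample-size figure changes.

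**What to change.** - Extend the daily shoe question already planned for the MS group to all patient groups in take-home testing. Controls who compare footwear need no change on this account, because footwear is their test condition.
- Report shoe mix by device period for each group.
- Keep the comparison of devices as used as the primary analysis. Add a sensitivity analysis that either restricts the comparable bouts to the same shoe or includes shoe as a factor. State this for the MS group too.

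Cost: one short item on a form already foreseen, a minor amendment with questionnaire approval, a slight daily burden on participants, and fewer bouts in the sensitivity analysis.
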